2.2.2 Truebinding, Inc. Investigational Product Background: TB006

Galectins are a ubiquitous group of proteins found in a variety of cells and tissues and are involved in numerous metabolic processes and functions. At least 15 galectin isotypes have been identified in epithelial cells of the respiratory system, digestive tract, urinary tract, skin, cardiovascular system, liver, immune cells, and in the CNS. Gal-3 plays an important role in different pathogenic conditions, including in neuroinflammatory and neurodegenerative disorders such as multiple sclerosis, AD, Parkinson's disease, and Huntington's disease. In addition, Gal-3 also plays a protective role due to its anti apoptotic effect in target cells. In vivo data from several investigators suggest that Gal-3 may be an important therapeutic target in pathological conditions including the disorders of the CNS.

TB006 is a humanized IgG4 (S228P) type monoclonal antibody that is highly specific and has high affinity to human Gal-3. It has demonstrated the potential to treat neurodegenerative disorders such as AD and traumatic brain injury, with an apparent wide safety margin, in preclinical models.

Detailed information can be found in the TB006 IB (see latest available version of IB).

Protocol TB006AD2102

Protocol Date and Version: 15 Oct 2021; v 3.0

2.3 Benefit/Risk Assessment

Based on preclinical pharmacology data and nonclinical toxicity studies with TB006, the overall benefit/risk profile favors clinical development of TB006 for treatment of AD.

More detailed information about the known and expected benefits and risks of TB006 based on data from the preclinical program may be found in the IB.

2.3.1 Risk Assessment

A standard battery of toxicology studies was conducted with TB006. The pivotal safety assessment was a 1 month GLP toxicology study in cynomolgus monkeys. Doses ranged from 10 to 200 mg/kg, and evaluation included clinical and laboratory observations, a 5 week recovery period, and full histopathology. No treatment related adverse findings were observed. Mild lymphoid hyperplasia occurred in males at the 10, 100, and 200 mg/kg dose levels, but based on mild severity, lack of dose dependency and historical test facility data from similar studies in cynomolgus monkeys, this finding was considered a species specific mild, reactive immune response and not an adverse toxicological finding. It is likely an immunogenicity reaction. No other findings were observed in this or any of the other toxicology studies.

TB006 is a first in class monoclonal antibody, therefore there are no known class adverse effects or risks to report from clinical studies. In general, risks associated with other monoclonal antibodies include allergic reactions such as hives or itching, flu like symptoms such as chills, fatigue, fever, and muscle aches and pains, nausea and vomiting, skin rashes and decreases in blood pressure. These effects have not been observed in preclinical studies to date. Other marketed IgG4 humanized monoclonal antibodies, such as natalizumab, eculizumab, and pembrolizumab, are used clinically. These antibodies largely target the immune system. There appears to be a spectrum of target-related negative effects when the total antibody dose gets too high. This pattern is not evident with TB006 in the preclinical toxicology profile, but will be closely observed in Phase 1 studies.

When performed correctly and according to industry standards, venipuncture complications are rare. However, even when properly performed, complications can include fainting, dizziness, hematoma, nerve injury, and arterial puncture or laceration. Blood draws and administration of the IV infusion in this study will be performed adequately trained medical staff to minimize any risk to patients.

Risks associated with a lumbar puncture can include headache, pain or numbness, bleeding, infection, puncture pain, and herniation. The lumbar puncture procedure will be performed by medical staff experienced with the technique and using aseptic techniques to minimize any risk to patients.

MR images are performed without the use of ionizing radiation, so patients are not exposed to the harmful effects of ionizing radiation. AEs for MRI scans are very rare. Millions of MRI scans are performed in the US every year, and the FDA receives around 300 AE reports for MRI scanners and coils each year from manufacturers, distributors, user facilities, and patients. The majority of these reports describe heating and/or burns (thermal injuries). To produce good

Protocol TB006AD2102

Protocol Date and Version: 15 Oct 2021; v 3.0

quality images, patients must generally remain very still throughout the entire MRI procedure. The MRI procedure will be performed by medical staff experienced with the equipment and the technique to minimize any risk to patients.

The safety assessments to be performed in this study, including clinical chemistry, hematology and urinalysis analyses, vital signs, ECGs, physical and neurological examinations, and assessments of AEs, SAEs, and C-SSRS are standard evaluations to ensure patient safety in this clinical study.

2.3.2 Benefit Assessment

TB006 is a humanized IgG4 (S228P) type monoclonal antibody that is highly specific and has high affinity to human Gal-3. It has demonstrated efficacy in preclinical models of neurodegenerative disorders such as AD and traumatic brain injury, and results are consistent with or superior to other compounds that have advanced into late-stage clinical studies. Thus, there is potential for TB006 to be effective in these disorders. The preclinical safety profile of TB006 supports the further investigation of TB006 in clinical studies.

Understanding that this therapy may have no clinical benefits to patients themselves, patients in this study will contribute to the process of developing new therapies in an area of unmet need.

Patients will undergo clinical evaluations/assessments associated with study procedures (eg, safety laboratory tests, vital sign and ECG measurements, and physical and neurological examinations), which would be a potential benefit for their own health awareness.

During confinement in the clinic, meals and access to forms of entertainment will be provided to patients. Patient expenses for time, travel, and other costs will be offset by a monetary compensation, consistent with standards for such study participations and after approval from the IRB to ensure that no coercion or undue influence are imposed on patients.

2.3.3 Overall Benefit Risk Conclusion

The above benefit risk assessment supports the conduct of this clinical study.

The preclinical data on TB006 to date suggests a wide margin of safety and minimal risk of adverse effects. The risks associated with study procedures, including lumbar puncture and blood draws, are also very low. Any potential adverse effects associated with the study drug and procedures are further minimized by intense safety monitoring and medical oversight by the investigator and study staff. Therefore, the potential risks identified in association with TB006 are justified by the anticipated benefits that may be afforded to patients with AD, if TB006 is successfully developed.

This study will be the second clinical study conducted with TB006. This study will be conducted in parallel and combined with the Phase 1 SAD study (Protocol number TB006HV1101). Each group in this study will commence after the safety, tolerability, and available PK of the single dose equivalent to the combined total of 5 qw doses planned in this study has been established.

Protocol TB006AD2102

Protocol Date and Version: 15 Oct 2021; v 3.0

3 OBJECTIVES AND ENDPOINTS

Table 3. Objectives and Endpoints

O	BJECTIVES - PART 1	ENDPOINTS
Pr	imary	
•	To determine the safety and tolerability of multiple doses of TB006	Safety endpoints, including the incidence of AEs and SAEs, clinical laboratory parameters, vital signs, ECGs, C-SSRS, and physical and neurological examinations, until Day 104 after the first TB006 dosing
•	To determine the PK profile of multiple doses of TB006	 PK parameters derived by noncompartmental analysis using the TB006 plasma concentration-time data, including, but not limited to and as appropriate: AUCtau: area under the concentration-time curve over a dosing interval Cmax: maximum observed plasma concentration tmax: time at which maximum plasma concentration occurs Ctrough: concentration at the end of a dosing interval t½: terminal elimination phase half-life CL: total clearance Vd: volume of distribution Extent of CSF distribution as estimated by TB006 CSF concentrations
•	To determine the maximum tolerated dose of multiple doses of TB006	Safety endpoints as above
•	To assess the immunogenicity of TB006 (production of anti-TB006 antibody)	Detection of anti-TB006 antibodies
•		Change from baseline through end of study on the Clinical Dementia Rating scale – Sum of Boxes total score

Protocol TB006AD2102

Protocol Date and Version: 15 Oct 2021; v 3.0

	 Change from baseline through end of study on the Cognitive Drug Research system battery score, composite scores and individual task measures Change from baseline through end of study on the MMSE score Change from baseline through end of study on the NPI score
--	---

OBJECTIVES - PART 2	ENDPOINTS
Primary	
To determine the clinical efficacy of TB006 in patients with mild to severe AD	Change from baseline through Day 104 on the Clinical Dementia Rating scale – Sum of Boxes total score
Secondary	
To determine the clinical efficacy of TB006 in patients with mild to severe AD	 Change from baseline through Day 36 on the Clinical Dementia Rating scale – Sum of Boxes total score Proportion of responders on the Clinical Dementia Rating scale – Sum of Boxes at Days 36 and 104 Change from baseline to Days 36 and 104 on the Cognitive Drug Research System Battery, composite scores and individual task measures Change from baseline to Days 36 and 104 on the MMSE score Change from baseline to Days 36 and 104 on the NPI score

Protocol TB006AD2102

Protocol Date and Version: 15 Oct 2021; v 3.0

PK = pharmacokinetic(s); SAE = serious adverse event.

To determine the safety and tolerability of multiple doses of TB006	Safety endpoints, including the incidence of AEs and SAEs, clinical laboratory parameters, vital signs, ECGs, C-SSRS, and physical and neurological examinations, until Day 104 after the first TB006 dosing
To determine the PK following multiple doses of TB006	 PK parameters including, but not limited to, by C_{trough}, C_{max}, and t_½.
CSF = cerebrospinal fluid; D = Day; ECG = electrocardiog	dverse events; C-SSRS = Columbia Suicide Severity Rating Scale; gram; MMSE = Mini Mental State
Examination; NPI = Neuropsychiatric Inventory;	PD = pharmacodynamic(s);

Protocol TB006AD2102

Protocol Date and Version: 15 Oct 2021; v 3.0

Part 2 will commence after the last patient in Part 1 has received their first dose. The planned dose in Part 2 will be 1,000 mg qw × 5 doses, but may be adjusted depending on the safety and tolerability of the doses in Part 1. Patients will be randomized to active TB006 or placebo (1:1) and will follow the same dosing schedule and procedures (with some exceptions – see SoA) as in Part 1. Randomization in Part 2 will be stratified according to baseline patient severity, with mild AD patients (MMSE 21-24) and moderate-severe AD patients (MMSE < 20) in each strata.

This is an outpatient study. Patients will return to the clinic for screening and baseline procedures, on dosing days, and on follow-up visits. Patients will have the option of checking into the clinic and staying overnight on Day -2 or Day -1, as well as on days prior to the other dosing days.

Protocol TB006AD2102

Protocol Date and Version: 15 Oct 2021; v 3.0

Study assessments will be conducted, and patients will be dosed according to the SoA (Table 1 and Table 2). Assessments for safety and tolerability, efficacy, PK, and PD are performed throughout the study (see Section 8). If a patient reports any AEs, they may be required to return to the clinical unit at the discretion of the investigator for additional assessments. All AEs must be followed to adequate resolution.

4.1.1 Study Duration for Participation

Each patient will be screened for eligibility up to 28 days prior to dosing, and study assessments will be performed up to 104 days after the first dose. The total study duration for each patient will therefore be up to approximately 19 weeks.

4.1.2 Number of Participants

In Part 1, 8 patients will be enrolled into each dose group, thus a total of approximately 24 patients will be randomized in this portion of the study (see Section 6.4.2 for details on randomization). In Part 2, 116 patients will be enrolled; 58 into active TB006 treatment and 58 to placebo.

The sample size determination is presented in Section 9.2.

4.1.3 Replacement of Patients

Patients who discontinue early from Part 1 of the study may be replaced, depending on when the discontinuation occurs. Replacement patients will receive the same treatment to which the discontinued patient was assigned. Patients who discontinue from Part 2 of the study will not be replaced.

4.1.4 Number of Sites

There are approximately 12 to 15 sites in this multi-center study, all in the US.

4.2 Scientific Rationale for Study Design

This is a seamless, two-part, Phase 1b/2a combined MAD and proof of concept study to assess the safety, tolerability, efficacy, PK, and PD of TB006 in AD patients.

An AD patient population is included in the study to determine the safety and tolerability of TB006 in the patient population that is being pursued for development. A mild to severe patient population is the tentative population of interest because they have the greatest medical need of the AD population and afford a large opportunity for improvement. TB006 may do more than simply halt disease progression. If it can improve cognition, the mild to severe population is where it is most likely to be detected. Patients with significant comorbidities are excluded to avoid confounding the interpretation of safety data.

Randomization will be used in this study to avoid bias in the assignment of patients to treatment, to prevent introducing bias into evaluations, to increase the likelihood that known and unknown patient attributes (eg, demographics and baseline characteristics) are balanced across dose groups, and to ensure the validity of statistical comparisons across treatment groups.

Protocol TB006AD2102

Protocol Date and Version: 15 Oct 2021; v 3.0

In Part 1, 8 patients per dose group (6 patients randomized to TB006 and 2 patients to placebo) are considered adequate to evaluate initial safety and PK in AD patients, and to support dose escalation decisions. In Part 2, patients will be randomized to TB006 or placebo in a 1:1 ratio (stratified by MMSE score at baseline [≤ 20 and 21-24]) so that approximately 58 patients are assigned to each group. Part 2 will assess the efficacy of TB006 on cognition using the Clinical Dementia Rating Scale − Sum of Boxes as the primary endpoint. Patients enrolled at the same dose level in Part 1, as well as all placebo patients, will be included in the efficacy analyses in Part 2.

Dose escalation decisions in Part 1, as well as dose selection for Part 2, will use safety, tolerability, and available PK data through the first dose administered to the last patient in each group and single dose safety and tolerability data from the SAD study (Protocol number TB006HV1101).

All clinical and laboratory assessments are standard measurements commonly used in Phase 1 studies to ensure patient safety.

Serial sampling to evaluate the repeat-dose PK profile of TB006 will be applied in Part 1 of this study, sparse sampling will be used in Part 2.

The interleave design with the SAD study is to ensure an efficient completion of the Phase 1 studies, while ensuring that safety and tolerability at the exposures in this study are adequately established in the SAD study.

Biomarkers specific to AD, such as	as well as nonspecific
biomarkers such as ,	are being collected and measured to assess target binding and
target engagement. Patients will per	form a battery of cognition tests, including the MMSE, the
Cognitive Dementia Rating Scale, t	he Cognitive Drug Research system battery, and the NPI
throughout the study to assess cogn	ition.

The rationale for the selection of doses in this study is described in Section 4.3.

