Part 2 will commence after the last patient in Part 1 has received their first dose. The planned dose in Part 2 will be 1,000 mg qw × 5 doses, but may be adjusted depending on the safety and tolerability of the doses in Part 1. Patients will be randomized to active TB006 or placebo (1:1) and will follow the same dosing schedule and procedures (with some exceptions – see Part 2 SoA) as in Part 1. Randomization in Part 2 will be stratified according to baseline patient

Protocol TB006AD2102

Protocol Date and Version: 15 Oct 2021; v 3.0

severity, with mild AD patients (MMSE 21-24) and moderate-severe AD patients (MMSE \leq 20) in each strata.

This is an outpatient study. Patients will return to the clinic for screening and baseline procedures, on dosing days, and on follow-up visits. Patients will have the option of checking into the clinic and staying overnight on Day -2 or Day -1, as well as on days prior to the other dosing days.

Assessments for safety and tolerability, efficacy, PK, and PD are performed throughout the study. If a patient reports any AEs, they may be required to return to the clinical unit at the discretion of the investigator for additional assessments. All AEs must be followed to adequate resolution.

Disclosure Statement: This is a randomized, placebo-controlled, sequential and parallel group treatment study that is patient and investigator blinded.

Number of Participants:

In Part 1, 8 patients will be enrolled into each dose group, thus a total of approximately 24 patients will be randomized in this portion of the study. In Part 2, 116 patients will be enrolled, 58 into active TB006 treatment and 58 to placebo.

Dose Groups and Duration:

In Part 1, three dose groups are planned, each representing one dose level of TB006 or placebo. In Part 2, two groups (active TB006 and placebo) are planned.

Each patient will be screened for eligibility up to 28 days prior to first dosing, and study assessments will be performed up to 104 days after first dosing. The total study duration for each patient will therefore be up to approximately 19 weeks.

[figure not shown]
Data Monitoring/Other Committee: In Part 1 only

Protocol TB006AD2102

Protocol Date and Version: 15 Oct 2021; v 3.0

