Blood sample for ApoE4 genotyping	X																	Optional ApoE4 sampling is collected at screening but can be taken at any visit until the last study visit (Section 8.7)
					J	Phar	maco	kinet	ics ar	ıd Ph	arm	acody	ynam	ics				
Blood sample for ADA assessment				X		X								X		X		ADA assessment is performed on blood sample collected for PK assessments; D1 and D8 assessment is performed on the pre-dose sample
Lumbar puncture for CSF collection ^e			х											X				Lumbar puncture indicated for D-1 can be performed any time between D-8 and D-1 CSF biomarkers, and TB006 levels will be determined in CSF

AD = Alzheimer's Disease; ADA = anti-drug antibody; AE = adverse event; anti-HCV = hepatitis C virus antibody; ApoE4 = apolipoprotein E4; COVID = coronavirus disease; CRF = case report form; C-SSRS = Columbia Suicide Severity Rating Scale; CSF = cerebrospinal

fluid; D = Day; DSM-5 = Diagnostic and Statistical Manual of Mental Disorders, Fifth Edition; ECG = electrocardiogram; E/D = Early Discontinuation;

HBsAg = hepatitis B surface antigen; IgM anti-HBc = immunoglobulin M antibody to hepatitis B core antibody; IV = intravenous(ly); MMSE = Mini-Mental State Examination;

NINCDS-ADRDA = National Institute of Neurological and Communicative Disorders and Stroke –

Alzheimer's Disease and Related Disorders Association; NPI = Neuropsychiatric Inventory; PD = pharmacodynamic(s);

PK = pharmacokinetic(s); SAE = serious adverse event.

CONFIDENTIAL Page 24 of 101

a Visit days and procedures are allowed a window of \pm 2 days from Day 1 to End of Treatment.

Protocol TB006AD2102

Protocol Date and Version: 15 Oct 2021; v 3.0

b Applicable only for patients who discontinue early from the study.

- c The medical history assessed at the screening visit should include prior AD treatment assessment(s). Establishing the clinical diagnosis of AD should include use of criteria from the DSM-5 Criteria for Major Neurocognitive Disorder (previously dementia) (Section, 10.4, Appendix 4) and the NINCDS-ADRDA (Note: ADRDA is now the Alzheimer's Association) (Section 10.5, Appendix 5).
- d The Cognitive Drug Research battery is to be performed twice during the screening visit in both Part 1 and Part 2.
- e The lumbar puncture procedure is optional.

f

Protocol TB006AD2102

Protocol Date and Version: 15 Oct 2021; v 3.0

	.2a						St	udy I)rug	Adm	inistr	ation	Peri	iod				Notes

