9.6 Safety Review Committee

An SRC will be involved in the conduct of this study. The SRC will be comprised of the PI and sponsor representatives including the Medical/Scientific Monitor, pharmacokineticist, statistician and others as deemed necessary. The SRC will review safety and available PK data on each accruing dose group after the last patient in each group has received their first dose. Safety, tolerability, and available PK data when the last patient in each group receives the first dose of study drug, will be used for dose escalation decisions. Also, each group in this study will commence after the safety, tolerability, and PK of the single dose equivalent to the combined total of 5 qw doses planned in the SAD study (Study TB006HV1101) has been established (minimum of 14 days from last patient dosing). Data will be reviewed by a blinded SRC. A decision will be made by the committee to either continue dosing for the next group at the planned dose level, continue at a modified dosing schedule, or to discontinue any dose escalation (and discontinue the study).

Safety reasons that could halt dose escalation are discussed in Section 6.2.1.

As needed, details of the responsibilities and organization of the SRC will be provided in a separate document.

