11.5. INTERIM ANALYSIS

No formal interim analysis planned for this study.

A SRC will meet for each dose cohort before continuing to the next dose cohort.

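### No dated safety committee review covers Group 3's completed five-dose 1,000 mg regimen before or during Part 2; the residual gap is narrow and cheap to close

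*Protocol*

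**What the plan says.** Three statements set the timing. On the choice of dose, Protocol 4.2 says that "dose selection for Part 2, will use safety, tolerability, and available PK data through the first dose administered to the last patient" in each group, together with single-dose data from the SAD study. On the start, Protocol 4.1 says "Part 2 will commence after the last patient in Part 1 has received their first dose". On review, Protocol 9.6 has the SRC "review safety and available PK data on each accruing dose group after the last patient in each group has received their first dose". SAP 11.5 agrees: "A SRC will meet for each dose cohort before continuing to the next dose cohort".

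The committee's remit is worded for escalation. Protocol 9.6 says "A decision will be made by the committee to either continue dosing for the next group at the planned dose level", with a modified schedule or an end to escalation as the alternatives. The Synopsis entry reads "Data Monitoring/Other Committee: In Part 1 only".

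Immunogenicity is a primary Part 1 objective (Protocol 3, Table 3). The Part 1 schedule (Protocol 1.3, Table 1) marks ADA on Days 1, 8, 36 and 104, with the note "ADA assessment is performed on blood sample collected for PK assessments; D1 and D8 assessment is performed on the pre-dose sample". ADA is not named among the SRC's inputs in Protocol 6.2.1 or 9.6.

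Other sections widen the oversight without dating it:

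- Protocol 6.2 brings safety, tolerability and available PK data from this study into the Part 2 dose choice.
- Protocol 6.2.1 has the SRC weigh related moderate or severe events, SAEs and discontinuations as they arise during treatment.
- Protocol 8.3.1 requires SAEs to reach the sponsor within 24 hours.
- Protocol 8.3.5 has the SRC monitor disease-related events routinely.
- Protocol 9.6 allows a separate SRC document if needed; it is not among the documents available here.

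**The concern.** Part 2 plans 58 active patients on 1,000 mg weekly for five doses. Only six active patients receive that regimen beforehand, and the dated review can fall when the last of them has had one infusion. A single SAD dose, however large, cannot show reactions or antibodies that need re-exposure. Group 3's remaining infusions and most of its Day 36 ADA and PK results come after the review, and no visible section sets a date on which the SRC sees them. They reach the committee only if an event prompts it, while Part 2 patients are being dosed.

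**Working it through.** The plan gives no figure of its own for this point, so the check is calendar arithmetic.

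**Inputs.** Eight patients per group, 6 active and 2 placebo (Protocol 6.4.1). Doses on Days 1, 8, 15, 22 and 29, so dose 5 falls 28 days and Day 36 falls 35 days after dose 1 (Protocol 1.3). About 1 patient per site per month at 4 sites in Part 1, that is 4 a month (Protocol 10.6, rationale for the escalation rule). A month is taken as 30.4 days.

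**Group 3 at the dated review, even spacing.** The gap is 30.4/4 = 7.6 days. Days since each patient's own first dose: 53.2, 45.6, 38.0, 30.4, 22.8, 15.2, 7.6, 0. Doses received: 5, 5, 5, 5, 4, 3, 2, 1, which is 30 of 40.

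- Five doses given (28 days or more): 4 of 8, on average 4 × 6/8 = 3 active.
- Day 36 reached (35 days or more): 3 of 8, on average 3 × 6/8 = 2.25 active.

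Other rates, for five doses and Day 36 respectively: 6 and 5 of 8 at 2 a month; 0 and 0 at 8 a month.

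**Random arrivals at 4 a month.** With exponential gaps of mean 7.6 days, on average 1.9 of 6 active patients have reached Day 36, and the chance that none has is 22%.

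**Groups 1 and 2.** Group 3 starts only after Group 2's last patient has had a first dose. With even spacing Group 3 then takes 7 × 7.6 = 53.2 days to fill, more than 35. So all 12 active patients in Groups 1 and 2 who continue are past Day 36. At 8 a month the figure is 26.6 days, and this would not be assured for Group 2.

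**Detection: chance of at least one reaction among the active patients reviewed, if each has a 20% risk (assumption).** The number active among those exposed is hypergeometric.

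| Reaction appears | At dated review, Group 3 only | All 6 active | Gain |
|---|---|---|---|
| From dose 2 (7 of 8 exposed) | 1 − (0.25 × 0.8^6 + 0.75 × 0.8^5) = 68.9% | 1 − 0.8^6 = 73.8% | 5 points |
| Only at dose 5 (4 of 8 exposed) | 1 − (15 × 0.8^2 + 40 × 0.8^3 + 15 × 0.8^4)/70 = 48.3% | 73.8% | 26 points |

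Those gains count 1,000 mg patients only. If the 12 lower-dose patients carry the same 20% risk, the probability of missing the reaction is multiplied by 0.8^12 = 0.0687:

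- From dose 2: 1 − 0.0687 × 0.311 = 97.9%, against 1 − 0.8^18 = 98.2%; gain 0.3 points.
- Only at dose 5: 1 − 0.0687 × 0.5175 = 96.4%, against 98.2%; gain about 2 points.

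**Peak exposure.** In a one-compartment model with r = 2^(−7/t), the fifth-dose peak is (1 − r^5)/(1 − r) times the first: 2.37 at t = 10 days and 2.61 at 12 days, the monkey half-lives in Protocol 4.3. The 5,000 mg single-dose peak is therefore 5/2.37 = 2.1 to 5/2.61 = 1.9 times the fifth-dose peak. Protocol 4.3 expects a longer half-life in humans; at an assumed 28 days the ratio is 5/3.64 = 1.4. SAD covers peak level throughout; it does not cover re-exposure.

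**Part 2 patients still undosed at the proposed review.** Assume Part 2 opens at once and enrols 1 per site per month at the 12 to 15 sites of Protocol 4.1.4. By 35 days, 12 × 35/30.4 = 13.8 to 15 × 35/30.4 = 17.3 have started, 6.9 to 8.6 of them active. About 49 to 51 of 58 active patients are then undosed, or 46 to 48 after two weeks of data preparation (assumption).

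**The case against.** The strongest reply is that the timing is deliberate and reasoned. Protocol 10.6 rests it on SAD cover to 5,000 mg, lower exposure from divided doses, and slow enrolment that lets follow-up accumulate. The arithmetic bears out the exposure argument and, in part, the accumulation argument. Monkeys received five weekly doses; their mild lymphoid hyperplasia was judged non-adverse and not dose-dependent, though Protocol 2.3.1 thinks it likely an immunogenicity reaction.

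Two stronger readings are tempting and do not hold. A reader might infer that no human repeat-dose data exist when the Part 2 dose is chosen. The sequential groups supply 12 active patients with the full regimen at lower doses, and Protocol 6.2 admits their data. A reader might also infer that SRC oversight ends at the last patient's first dose. Protocol 6.2.1 and 8.3.5 give it continuing though undated roles, Group 3 patients remain Part 1 patients to Day 104, and SAEs reach the sponsor within a day. An overt reaction in 20% of patients would probably surface that way, so the detection gains above overstate the benefit for such events.

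The separate SRC document might also already set the date. What survives is that none of these visibly schedules a look at the completed 1,000 mg regimen, and none brings ADA, post-regimen PK or the cumulative non-serious pattern to the committee.

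**Conclusion.** The point holds in a limited form. No visible section dates an SRC review of Group 3's complete five-dose safety, PK and ADA data. The gap is confined to effects specific to 1,000 mg, silent ADA or PK changes after the full regimen, and the build-up of non-serious events. The 26-point gain applies only to a reaction specific to 1,000 mg that appears only at dose 5; if lower doses are informative, the gain is at most about 2 points. Neither figure measures silent ADA or PK change. The results rest on the stated enrolment rate, even spacing and an assumed 20% risk. This is an inexpensive improvement to consider; it does not show that the Part 2 dose is unsafe or the escalation rule unsound. Confidence is medium, mainly because the SRC document is unseen.

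**What to change.** Add to Protocol 9.6: *Once the last Group 3 patient reaches Day 36, the SRC will also review cumulative blinded Group 3 safety data, with available PK and ADA results pooled so that no individual assignment is revealed. Part 2 enrolment continues meanwhile. The SRC may recommend pausing Part 2 or lowering its dose.* Amend the committee line in the Synopsis to match. Show no efficacy data, because Part 1 patients at the Part 2 dose enter the Part 2 efficacy analysis (Protocol 9.4.5). Pooling respects the restriction on unblinding concentration data in Protocol 8.5. If a separate SRC document already sets this review, citing it in 9.6 is enough.

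The cost is one extra meeting on data already being collected, with no enrolment delay. The last patients' ADA results may arrive after the meeting and would follow as a supplement. If a signal led to a lower dose, the active arm of the primary comparison would mix two doses; the Synopsis and Protocol 6.2 already permit dose adjustment.
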